## History of Changes

Version Number	Version Date	Notes
1.0	November 9, 2021	Final, submitted to the FDA.
2.0	December 13, 2021	
Amendment, to be submitted to the FDA.
 
The following changes are made per FDA feedback on SAP V1.0:
 

1) As per FDA guidance, the ITT definition was reverted back to the original definition to clarify unequivocally that all randomized subjects will be in the ITT analysis set.

2) For binary endpoints, specified the CMH test stratified by randomization strata as the main method for the 95% CI. Removed the 95% CI based on normal approximation.

3) Added sensitivity analysis using multiple imputation methods to handle missing data in binary endpoints.

4) Added details for tipping point analysis and reference.

 
The definition of NIAID at randomization and Day 1 NIAID are further clarified via some editorial changes.

## List of Abbreviations

---

2019-nCoV	2019 novel coronavirus
AE	Adverse event
AESI	Adverse event of special interest
ALT	Alanine aminotransferase
ARDS	Acute respiratory distress syndrome
AST	Aspartate aminotransferase
ATC	Anatomic-therapeutic-chemical
BiPAP	Bi-level positive airway pressure
CMH	Cochran-Mantel-Haenszel
COVID-19	Corona Virus Disease 2019
CPAP	Continuous positive airway pressure
CRF	Case report form
CRP	C-reactive protein
CT	Computerized tomography
ECG	Electrocardiogram
ECMO	Extracorporeal membrane oxygenation
EDC	Electronic Data Capture
eCRF	Electronic case report form
FiO 2	Fraction of inspired oxygen
ICU	Intensive care unit
IL	Interleukin
IMV	Invasive mechanical ventilation
IRT	Interactive Response Technology
LDH	Lactate dehydrogenase
MedDRA	Medical Dictionary for Regulatory Activities
MERS	Middle East respiratory syndrome
ITT	Modified intent-to-treat
NIAID	National Institute of Allergy and Infectious Diseases
PaO 2	Partial pressure of oxygen
PCR	Polymerase chain reaction
PD	Pharmacodynamics
PEEP	Positive end-expiratory pressure
PK	Pharmacokinetics
PT	Preferred term
qSOFA	Quick sequential organ failure assessment
SAP	Statistical analysis plan
SOC	System organ class
SOFA	Sequential Organ Failure Assessment Score
TEAE	Treatment-emergent adverse event

---

## 1. INTRODUCTION

This Statistical Analysis Plan (SAP) describes the statistical analyses and data presentation to be performed for the Phase 3 part of the study KPL-301-C203 by Cohort. The efficacy endpoints are based on protocol amendment 6.0 dated November 8, 2021; while the data collection and visits might reflect previous versions of the protocol depending on the reconsent date. Selected outputs supporting efficacy of pooling Phase 2 and Phase 3 parts of the study by Cohort are covered under this SAP.

It contains definitions of analysis populations, derived variables, and statistical methods for the analyses of efficacy and safety. It is to ensure that the data listings, summary tables, and figures which will be produced, and the statistical methodologies that will be used, are complete and appropriate to allow valid conclusions regarding the study objectives.

The SAP will be finalized and approved prior to the clinical database lock (DBL) for the primary analyses when the last subject in Cohort 1 completes Day 29. A follow-up analysis will be conducted at the end of a 90-day safety follow-up period for all subjects. Cohort 1 and 2 will be analyzed separately. The database locks might be combined for the two cohorts as appropriate.

Analyses of pharmacokinetics (PK), Pharmacodynamics (PD), other biomarkers, and health care resource utilization are outside the scope of this SAP and will be addressed separately.

### 1.1. Objectives

#### 1.1.1. Primary Objective

The primary objective of this study is to evaluate the clinical efficacy of a single intravenous (IV) dose of mavrilimumab (10 mg/kg or 6 mg/kg) relative to placebo in adult subjects hospitalized with severe Corona Virus Disease 2019 (COVID-19) pneumonia and hyper-inflammation to reduce progression to respiratory failure or death.

#### 1.1.2. Secondary Objectives

The secondary objectives of this study are to assess impact of treatment on clinical status, mortality, and safety of a single IV dose of mavrilimumab (10 mg/kg or 6 mg/kg) relative to placebo in adult subjects hospitalized with severe COVID-19 pneumonia and hyper-inflammation.

#### 1.1.3. Other Objective

[REDACTED]

[REDACTED]

[REDACTED].

### 1.2. Study Design

This is a prospective, Phase 2/3, interventional, randomized, double-blind, placebo-controlled study designed to evaluate the efficacy and safety of mavrilimumab (KPL-301) treatment in adult subjects hospitalized with severe COVID-19 pneumonia and hyper-inflammation.

Screening activities will be performed up to 3 days prior to randomization. The study main follow-up period for efficacy will conclude on study Day 29, and subjects will be further followed for AEs/SAEs, concomitant medications, mortality, and clinical improvement (National Institute of

Allergy and Infectious Diseases (NIAID) scale) through study Day 90. The schedule of activities is presented in Table 2 of the protocol.

The Phase 3 part of the study will enroll approximately 600 subjects in Cohort 1 (581 subjects at time of enrollment closure) and 117 subjects in Cohort 2 (63 subjects at time of enrollment closure). Each cohort will randomize subjects in a 1:1:1 allocation ratio to receive a single IV infusion of mavrilimumab (10 mg/kg or 6 mg/kg) or placebo. Cohort 1 will include non-intubated hospitalized subjects who require supplemental oxygen to maintain  $\text{SpO}_2 \geq 92\%$ , i.e., “non-ventilated” subjects. Cohort 2 will include hospitalized subjects for whom mechanical ventilation was recently initiated (within 48 hours prior to randomization), i.e., “ventilated” subjects.

### 1.3. NIAID Scale

Subject clinical status will be assessed daily using the 8-point NIAID scale, which is the basis for assessment of primary and secondary endpoints for Cohort 1 and Cohort 2.

1. Death
2. Hospitalized, on invasive mechanical ventilation or extracorporeal membrane oxygenation (ECMO)
3. Hospitalized, on non-invasive ventilation or high flow oxygen devices
4. Hospitalized, requiring supplemental oxygen
5. Hospitalized, not requiring supplemental oxygen – requiring ongoing medical care (COVID-19 related or otherwise)
6. Hospitalized, not requiring supplemental oxygen – no longer requires ongoing medical care
7. Not hospitalized, limitation on activities and/or requiring home oxygen
8. Not hospitalized, no limitations on activities

### 1.4. Sample Size Justification

Sample sizes were calculated separately for each cohort based on their primary endpoint and other assumptions. Subjects will be randomized with a 1:1:1 allocation ratio within each cohort.

Sample size estimation for Cohort 1 (non-ventilated subjects) in Phase 3 is based on the primary efficacy endpoint proportion of subjects alive and free of mechanical ventilation at Day 29, using a Chi square test. The assumptions used for the calculation are adjusted based on the results of Phase 2 portion. Assuming the proportions of subjects alive and free of ventilation at Day 29 are 87.5% and 74.4% for the active treatment arm and placebo arm, respectively, approximately 200 subjects per arm will achieve a minimum 90% power for the treatment comparison at the two-sided alpha value of 0.05. A total of 600 subjects will be randomized. At the time of the enrollment closure, 581 subjects were randomized.

Sample size for Cohort 2 (ventilated subjects) in Phase 3 is based on the primary efficacy endpoint mortality rate at Day 29, using a Fisher’s exact test. Approximately 117 subjects will be randomized with a 1:1:1 allocation ratio. Assuming the mortality rates at Day 29 are 40% and 95% for the active treatment arm and placebo arm, respectively, 39 subjects per arm will achieve 90% power for the treatment comparison when the two-sided alpha value is 0.05. Sixty-three subjects were randomized at the time of enrollment closure.

[illegible]

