### **13.3.2. Phase 3**

Approximately 665 subjects will be randomized to the Phase 3 part of this study.

Sample size for Cohort 1 (non-ventilated subjects) of the Phase 3 part is determined based on the primary efficacy endpoint proportion of subjects alive and free of mechanical ventilation at Day 29 (mavrilimumab 6 mg/kg vs placebo), using the Chi square test. The assumptions used for the calculation are adjusted based on the results of Phase 2 portion. Approximately 600 subjects will be randomized with a 1:1:1 allocation ratio. Assuming the proportions for the active arm and placebo arm are 87.5% and 74.4% respectively, approximately 200 subjects per arm are sufficient to achieve at least 90% power for the treatment comparison at the two-sided significance level of 0.05.

Sample size for Cohort 2 (ventilated subjects) of the Phase 3 part is determined based on the mortality rate at Day 29 using a Fisher's exact test. Approximately 117 subjects will be randomized with a 1:1:1 allocation ratio. Assuming the mortality rates for the active arm and placebo arm are 40% and 80% respectively, approximately 39 subjects per arm are required to achieve a 90% power for a pairwise comparison versus control when the two-sided alpha value is 0.025. However, based on review of the Phase 2 Cohort 2 results of the primary and secondary endpoints at day 29, Phase 3 Cohort 2 is closed to further enrollment (approximately 65 subjects randomized at the time of enrollment closure), as there was no evidence that mavrilimumab provided clinical benefit over placebo in recently ventilated patients.

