### **5.7.1. Multiplicity Adjustment**

Multiplicity adjustment for Phase 3 Cohort 1 will be done to guarantee strong control of the overall Type I error rate at a two-sided alpha value of 0.05. For each endpoint, the test statistics for the two comparisons asymptotically follow a bivariate normal distribution and are positively correlated due to sharing a common control arm (placebo). Thus, the conventional Hochberg method will be used to adjust for multiplicity in the analysis of the two dose levels and the sequence of efficacy endpoints. Below are the details.

Considering the hypothesis testing of both the 10 mg/kg and the 6 mg/kg individually versus placebo for each endpoint to be a family, the testing on the primary endpoint and the three ordered secondary endpoints correspond to Family 1, Family 2, Family 3, and Family 4, respectively.

Testing will be done sequentially (Family 1, then 2, 3, and 4) based on the following decision rules (p-values are all two-sided):

- If both p-values in a family are  $\leq 0.05$ , statistically significant treatment effects for the endpoint can be claimed for both dose levels, and testing may proceed to the next family to test those hypotheses at two-sided significance level of 0.05.
- If the larger p-value is  $> 0.05$  and the smaller p-value is  $\leq 0.025$ , a statistically significant treatment effect can be claimed only for the one dose level corresponding to the smaller p-value. Sequential testing stops here, and no further inferential testing can be done. The remaining data analyses will be provided for completeness (with p values as nominal) to inform the discussion of benefit-risk.
- If both p-values in the family are  $> 0.05$ , a statistically significant treatment effect cannot be claimed for either dose level. Sequential testing stops here, and no further inferential testing can be done. The remaining data analyses will be provided for completeness (with p values as nominal) to inform the discussion of benefit-risk.

No multiplicity adjustment will be done for Phase 3 Cohort 2. No formal testing will be conducted as enrollment for this cohort stopped early.

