#### 5.7.4. Analysis of Primary Efficacy Endpoint

The proportion of subjects alive and free of ventilation at Day 29 for Cohort 1, and the proportion of subjects who die (mortality rate) by Day 29 for Cohort 2 will be analyzed by the CMH test adjusted for the actual randomization strata (Cohort 1: standard of care antiretroviral therapy, age, and ARDS status; Cohort 2: standard of care antiretroviral therapy and age). The 95% confidence interval (CI) will be calculated using the Clopper-Pearson exact method. Number of subjects and percentages will be summarized by treatment.

The CMH method addresses the global null hypothesis of no difference between treatments. Hence, it corresponds to the risk difference being 0, the risk ratio being 1, and the odds ratio being 1. The CMH

p-value is the same across odds ratio/risk ratio/risk difference. In addition to CMH p-value, the stratified risk difference, stratified relative risk, and the stratified odds ratio and their 95% confidence interval (CI) will be provided in our analyses.

Analysis of the primary efficacy endpoint based on the per-protocol population will be conducted following the same methods.

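### Phase 3 SAP 1.4 credits Cohort 2 with 90% power at 39 per arm for 40% vs 95% mortality; those inputs give 99.99%, and the 95% contradicts the protocol's 80%

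*Combined protocol and SAP*

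**What the plan says.** Phase 3 SAP 1.4 states that the Cohort 2 sample size "in Phase 3 is based on the primary efficacy endpoint mortality rate at Day 29, using a Fisher" exact test. It plans 117 subjects, allocated 1:1:1. Its assumptions read "Assuming the mortality rates at Day 29 are 40% and 95% for the active treatment arm and placebo arm, respectively, 39 subjects per arm", and it concludes that "39 subjects per arm will achieve 90% power for the treatment comparison when the two-sided alpha value is 0.05". It adds that 63 subjects had been randomized when enrollment closed.

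Protocol 13.3.2 has the same endpoint, test, total, number per arm and power, but different inputs: "Assuming the mortality rates for the active arm and placebo arm are 40% and 80% respectively, approximately 39 subjects per arm are required" for 90% power in a pairwise comparison with control at two-sided alpha 0.025. The protocol synopsis agrees with 13.3.2. The Phase 2 calculations for Cohort 2, in protocol 13.3.1 and in section 1.4 of the Phase 2 SAP, also assume 40% vs 80%.

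Protocol 13.4 sets the two-sided type I error rate at 0.05 for each Phase 3 cohort and makes no multiplicity adjustment for Cohort 2. On testing, Phase 3 SAP 5.7.1 says: "No formal testing will be conducted as enrollment for this cohort stopped early". Section 5.7.4 of the same SAP says that "the proportion of subjects who die (mortality rate) by Day 29 for Cohort 2 will be analyzed by the CMH test".

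**The concern.** Two documents give the same sample size and power from different placebo rates and different alphas. A difference of 55 percentage points (40% vs 95%) needs far fewer subjects than one of 40 points (40% vs 80%), so both statements cannot be right at 39 per arm. The legible text of SAP section 6, which lists changes from the protocol, does not mention new Cohort 2 assumptions. SAP 1.4 says that the Cohort 1 assumptions were adjusted after Phase 2 but says nothing similar for Cohort 2.

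What is at stake is how Cohort 2 is read, not how it was run. The SAP gives no power for the 63 subjects enrolled. A reader who works it out from the SAP's stated rates would get about 98% at 21 per arm and would take a null result as close to conclusive. With the protocol's rates the answer is 57% or 65%, depending on alpha.

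**Working it through.** **Inputs.** Phase 3 SAP 1.4: p(active) = 0.40, p(placebo) = 0.95, two-sided alpha 0.05, Fisher's exact test, n = 117/3 = 39 per arm, claimed power 90%. Protocol 13.3.2 and synopsis: the same, except p(placebo) = 0.80 and two-sided alpha 0.025. Size at closure: 63/3 = 21 per arm, assuming equal allocation.

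**Formula.** Exact power = sum over x and y from 0 to n of b(x; n, p1) × b(y; n, p2) × I[Fisher two-sided p(x, y) ≤ alpha], where b is the binomial probability and I is 1 if the condition holds and 0 otherwise.

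**Step 1: reproduce the protocol's figure.** With 40% vs 80% and alpha 0.025, n = 39 gives 90.2% and n = 38 gives 88.7%. So 39 per arm at 90% is reproduced exactly.

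**Step 2: apply the SAP's inputs.** With 40% vs 95% and alpha 0.05, n = 39 gives 99.99%. For 90% power, n = 15 gives 88.6% and n = 16 gives 91.3%, so 16 per arm is enough.

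A hand check uses the pooled normal approximation, power = Φ[(d − z × s0)/s1]:
- mean rate = (0.40 + 0.95)/2 = 0.675
- s0 = √(2 × 0.675 × 0.325/39) = 0.1061
- s1 = √((0.40 × 0.60 + 0.95 × 0.05)/39) = 0.0859
- (0.55 − 1.96 × 0.1061)/0.0859 = 3.98, and Φ(3.98) = 99.997%

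**Step 3: find which input breaks the calculation.** Exact Fisher results:

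| Placebo rate | Two-sided alpha | Power at 39 per arm | Smallest n per arm for 90% |
|---|---|---|---|
| 95% | 0.05 (SAP) | 99.99% | 16 |
| 95% | 0.025 | 99.97% | 18 |
| 80% | 0.05 | 93.8% | 33 |
| 80% | 0.025 (protocol) | 90.2% | 39 |

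Changing alpha alone does not rescue the SAP's statement. Even at alpha 0.0125, 40% vs 95% gives 99.93% at 39 per arm. Changing 95% to 80% brings the power to 93.8% at the SAP's own alpha. The placebo rate is therefore the input that fails.

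**Step 4: power at closure, 21 per arm, Fisher's exact test.**
- 40% vs 80%: 57.1% at alpha 0.025 and 65.4% at alpha 0.05.
- 40% vs 95%: 98.0% at alpha 0.05.

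**The case against.** The best defence is that almost nothing depends on this sentence. Enrollment in Cohort 2 had already been closed on the Phase 2 results, so SAP 1.4 is retrospective. With the SAP's inputs 39 per arm is more than enough, so the error could not have left the cohort too small. The number enrolled and the absence of formal testing are both disclosed, and the 95% confidence intervals planned in SAP 5.7.4 will show the imprecision. All of this stands, and it limits the point to a misstated justification.

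The defence also rules out some stronger readings that a reader might infer:

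- *That alpha 0.05 is a second error.* Protocol 13.4 sets 0.05 for each Phase 3 cohort, with no adjustment for Cohort 2. The value matches that section and differs only from the pairwise 0.025 in 13.3.2. It needs reconciling but is not shown to be wrong.
- *That 39 per arm can come only from alpha 0.025.* At 40% vs 80% and alpha 0.05, 33 per arm is needed, and 33/0.85 = 38.8, which rounds up to 39. The 15% dropout in that sum is borrowed from Phase 2 Cohort 1; none is stated for Phase 3 Cohort 2. This route also needs 80%, not 95%.
- *That 95% mortality is implausible.* The documents give no observed Cohort 2 rates against which to judge either 95% or 80%. What they show is that every other Cohort 2 calculation uses 80%.
- *That 57% is the power at closure.* It holds for Fisher's test at 0.025. The planned Phase 3 test is CMH, and the cohort-level alpha is 0.05. An unstratified normal approximation gives about 67% at 0.025 and 77% at 0.05.
- *That the CMH test should be deleted from SAP 5.7.4.* The statement on formal testing can be read as governing inference, with 5.7.4 describing the calculation. Deleting it there would leave CMH and log-rank comparisons in SAP 5.7.5 and protocol 13.2.4. A label settles the matter.

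**Conclusion.** The point holds as an error in the stated justification. SAP 1.4 pairs the protocol's sample size and power with a placebo rate that cannot produce them: the stated power is 90% and the computed power is 99.99%. The protocol's own inputs give 90.2%. The contradiction in placebo rate (95% vs 80%) is plain. The difference in alpha (0.05 vs 0.025) has to be reconciled across SAP 1.4, protocol 13.3.2 and protocol 13.4.

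The size is minor. Cohort 2 was closed and not undersized by this error, no decision rests on the sentence, and Cohort 1 is untouched. What remains is that a null Cohort 2 result could look stronger than it is, and that Cohort 2 p-values carry no nominal label. The SAP uses that label only in the Cohort 1 decision rules.

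The power figures assume independent binomial outcomes, equal arms, no dropout and an unstratified two-sided Fisher's exact test. The closure figures also assume 21 per arm.

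**What to change.** 1. In Phase 3 SAP 1.4, restate Cohort 2 with the protocol's inputs: 40% vs 80%, Fisher's exact test, two-sided alpha 0.025, 39 per arm, 90% power. If alpha 0.05 is kept, write 40% vs 80% with 39 per arm giving about 94%, and say how this relates to protocol 13.3.2. If 95% was intended, list and justify it in SAP section 6 and correct the power to above 99.9%.
2. If power at closure is quoted, name the test and alpha. For example: with 63 subjects (about 21 per arm) and 40% vs 80%, Fisher's exact test has about 57% power at two-sided 0.025 and 65% at 0.05.
3. In SAP 5.7.1, add that all Cohort 2 p-values, including those from 5.7.4 and 5.7.5, are nominal and that the results are descriptive. This agrees with protocol 13.4 and leaves the planned calculations as they are.

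The cost is two or three sentences of SAP text. No data, endpoint, analysis program or Cohort 1 inference changes.

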## 2.4. Safety Endpoints

The following are safety endpoints:

- Adverse events, adverse events of special interest, and serious adverse events
- Laboratory parameters
- Vital signs
- Electrocardiogram
- Chest x-ray or CT scan
- Physical examination

**Table 1: Summary of Primary, Secondary and Selected Other Efficacy Endpoints**

[illegible]

S: secondary efficacy endpoint; S1: first secondary endpoint; S2, S3: second, and third secondary endpoints, respectively.

Y: other efficacy endpoints.

\*: [REDACTED]

1

### **3. ANALYSIS SETS**

#### **3.1. Intent-to-Treat (ITT) Analysis Set**

All randomized subjects will be included in the ITT analysis set. All efficacy analyses of the study will be based on the ITT analysis set. All ITT analyses will be based on the randomized treatment.

#### **3.2. Safety Analysis Set**

All randomized subjects who receive study drug will be included in the safety analysis set. Safety analyses will be based on the actual treatment received.

#### **3.3. Per-Protocol (PP) Analysis Set**

All ITT subjects without protocol deviations deemed to impact efficacy or ethical conduct will be included in the PP analysis set and will be determined before the database lock. The primary and secondary efficacy endpoints will be further analyzed based on the PP set.

#### **3.4. Day 90 Analysis Set**

All ITT subjects who were randomized at least 90 days prior to the data cutoff date for the first database lock. Selected Day 90 efficacy endpoints, e.g., mortality will be analyzed based on Day 90 set and the randomized treatment.

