9	Tuberculosis screening is mandatory for South Africa sites and is at the discretion of the Investigator elsewhere. If required, one positive (or 2 indeterminate) interferon gamma release assay test results or one positive PCR test is exclusionary.
10	The NIAID score should be recorded at the time of randomization for all eligible subjects. For subjects in Cohort 1 only, also record 1) either PaO 2 (mmHg), if available, or SpO 2 (%), and 2) FiO 2 (%) for subjects on assistive ventilation or L/min of oxygen supplementation for subjects not on assistive ventilation (e.g., simple mask/cannula). Initiation of study drug administration should occur within 24 hours of randomization.
11	If the subject remains hospitalized after Day 8 these assessments should be collected daily until the day of discharge (ie, Days 9-14, 16-21, 23-28 or after Day 29). On Day 1, assessments should be collected at the time closest to and prior to the initiation of study drug administration. Daily collection guidelines after Day 1: collect assessment in the morning at approximately the same time each day and closest to the collection of the NIAID score assessment, except for respiratory parameters (see footnote #16)
12	If available, ECHO performed from 90 days prior to randomization through Day 90 will be collected (report only).
13	If discharged, these assessments must be performed via phone call at Days 15, 22, and 29.
14	The NIAID at discharge to home should reflect status immediately post-discharge (ie, either 7 or 8).
15	Collect ventilation supportive measures (eg, pronation, nitric oxide use, tracheostomy) received by subjects on mechanical ventilation; details in the Site Manual.
16	Respiratory function parameters will be recorded daily until the date of Discharge. Daily values based on the highest daily FiO 2 , including PaO 2 , FiO 2 , SpO 2 and oxygen requirement. Other arterial blood gas parameters if available should be recorded. In addition, other supportive measures including pronation, neuromuscular blockade, tracheostomy, ECMO, vasopressor or inotropic therapy, inhaled nitric oxide or other should be recorded.

Global Version 6 (Amendment 5)

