**Table 4: Schedule of Laboratory Assessments**

Activity / Parameter	Collection Detail	Collection Timepoints
CENTRAL LABORATORY		
Respiratory Panel	A/H3N2, A/H1N1pdm09, A/H7N9, A/H5N1, A, not typed, B, or other (specify); coronavirus – novel CoV, MERS CoV, other CoV (specify); RSV; adenovirus; bacteria; other infectious respiratory diagnosis (specify); clinical pneumonia	Screening
██████████	██████████	████████████████████ ████████████████████ ████████████████████
██████████ ██████████	████████████████████ ████████████████████ ████████████████████ ████████████████████ ████████████████████ ████████████████████	████████████████████ ████████████████████ ████████████████████
Anti-mavrilimumab antibody		Screening and the Discharge/UNS visit
Pharmacokinetic sample		Day 1 (before infusion and when infusion is complete), Days 3±1, 7±1, 15±2, 29+4 and at the Discharge/UNS visit
LOCAL LABORATORY		
Pregnancy test (women of child-bearing potential)	Urine or serum βhCG	Screening and at the Discharge/UNS visit; Day 90+14 is optional
██████████ ██████████		████████████████████ ████████████████████ ████████████████████
Hematology	Complete blood count + differential	Screening (up to 7 days prior to randomization), Days 3±1, 15±2, 29+4 and at the Discharge/UNS visit; Days 60+14 and 90+14 are optional
Coagulation	PT, PTT, and INR	
Chemistry	electrolytes, blood urea nitrogen, glucose and CR	
Liver Profile	AST, ALT, Alb, AlkP, Tbili, Dbili	

Activity / Parameter	Collection Detail	Collection Timepoints
Lipid Panel	Cholesterol, total; high-density lipoprotein (HDL) cholesterol; low-density lipoprotein (LDL) cholesterol (calculation); triglycerides; very low-density lipoprotein (VLDL) cholesterol (calculation)	Screening (up to 7 days prior to randomization) and at the Discharge/UNS visit
Urinalysis		Screening (up to 7 days prior to randomization) and Discharge/UNS visit; Day 29+4, Days 60+14 and 90+14 are optional
Tuberculosis		Optional at Screening - at Investigator's discretion South Africa only: TB testing required for all subjects at Screening
SARS-CoV-2	COVID-19	Screening* Days 1, 2, 3, 4, 5, 6, 7, 8, 15 ±2, 22 ±2, 29 +4 and Discharge/UNS are optional

Screening = up to 3 days prior to randomization

\*For SARS-CoV-2 testing (COVID-19), a positive test within 14 days of randomization is required. Sites that are unable to perform SARS-CoV-2 locally (at the clinical site or from another institution) may use Central Laboratory testing.

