### **4.2.2. Day 1**

**Day 1** is defined as the day of the study treatment after randomization.

For subjects without dosing, Day 1 is defined as the randomization date in the analysis of efficacy while endpoints points are defined by study day, like Day 29, Day 90 endpoints.

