#### **4.2.5. Calculation Using Dates**

Calculations using dates will adhere to the following conventions:

Study day for a date of interest (TARGET DATE) is calculated as

STUDY DAY = TARGET DATE – Date of Day 1 + 1 if TARGET DATE is on or after Day 1;

STUDY DAY = TARGET DATE – Date of Day 1 otherwise.

Day X in this document refer to the study day X, where X can be 4, 8, 15, 22, 29, 60, 90, etc.

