### **4.3. Windowing of Visits**

Data will be summarized by eCRF scheduled visits and allowed visit windows. When there are multiple assessments for a scheduled visit, the first non-missing value will be used. No additional windowing will be considered.

Due to changes of visit windows across protocol versions, the minimum window that can cover windows in all protocol versions will be used in the analysis of the efficacy endpoints: the window is (-2 days, + 2 days) for Day 15 endpoints, (-2 days, + 4 days) for Day 29 endpoints, (-7 days, +14 days) for Day 90 endpoints.

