#### **4.6. Data Cut-off Date**

Two DBLs are planned for Phase 3 Cohort 1:

- For the first DBL, unless otherwise specified, all analyses will be conducted based upon data through Day 29 for each subject instead of a fixed data cut-off date:
  - For Day 29 efficacy endpoints, a + 4-day window is allowed.
  - For Day 90 efficacy data, mortality rate will be produced.
  - Selected TEAE tables may be produced for a subgroup of subjects (for selected sites and randomization date) with complete TEAE data through Day 90.
  - Laboratory endpoints will only be analyzed for baseline values.
- For the second DBL, all analyses will be updated based on the complete study data. Data throughout Day 29 are expected to remain the same as the first DBL.

Only one DBL is planned for Phase 3 Cohort 2. All data through study completion/early discontinuation will be included.

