## 6. CHANGES TO PLANNED ANALYSES FROM THE PROTOCOL

- The following other efficacy endpoints are out of scope for this SAP, and will be reported separately
  - [REDACTED]
  - [REDACTED]
  - [REDACTED]
  - [REDACTED]
  - [REDACTED]
  - [REDACTED]
- All randomized subjects will be included in the ITT analysis set.
- Summary of Remdesivir and Corticosteroids Before Day 29 are added
- For favorable Day 29 endpoints, death will be censored at Day 35 instead of Day 30 as specified in the protocol
- The main analyses for the first database lock of Cohort 1 will not use a fixed data cut-off date. Subject level Day 29 dates will be used instead.
  - Efficacy endpoints based on Day 29 will consider data through Day 29 window.
  - Non-efficacy parameters that involve data after Day 29 by definition, e.g., TEAE, CM, will only include data through Day 29 in the first database lock.
  - Lab summary tables will only include baseline; and lab shift tables will not be provided since only baseline lab data will be cleaned in the first DBL.

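### At the first lock of Phase 3 Cohort 1, the Day 90 set admits subjects 13 to 14 days before the SAP's Day 90 window closes, with no defined cut-off date and no outcome rule for pending subjects

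*Combined protocol and SAP*

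**What the plan says.** **Entry rule.** Phase 3 SAP 3.4 admits "All ITT subjects who were randomized at least 90 days prior to the data cutoff date for the first database lock". Section 4 applies this set to selected Day 90 efficacy endpoints at the Day 29 lock, and Section 4.6 lists Day 90 mortality among that lock's outputs. The full ITT set is used for Day 90 endpoints at the later lock.

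**Window.** SAP 4.3 runs the analysis window from minus "7 days, +14 days) for Day 90 endpoints", that is, study Days 83 to 104. The current protocol allows only the later side (Schedule of Activities; Table 4, "Days 60+14 and 90+14 are optional" for laboratory tests).

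**Study day.** SAP 4.2.2: Day 1 "is defined as the day of the study treatment after randomization". SAP 4.2.5 counts a study day as the target date minus the date of "Day 1 + 1 if TARGET DATE is on or after Day 1". Protocol Schedule of Activities, footnote 10: "Initiation of study drug administration should occur within 24 hours of randomization".

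**Cut-off.** Sections 3.4 and 4.2.4 (last date known alive) both depend on a data cut-off date. Section 4.6 says that at the first lock, unless something else is specified, "all analyses will be conducted based upon data through Day 29 for each subject instead of a fixed data cut-off date". Section 6 says "The main analyses for the first database lock of Cohort 1 will not use a fixed data cut-off date".

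**Mortality rule.** SAP 5.7.2 counts a subject as alive in three cases: last known alive on or after the target day, last known alive earlier but inside the window, or terminated early for a reason other than death.

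**The concern.** The purpose of the set is to hold subjects whose Day 90 status can be known at the first lock. Someone randomized exactly 90 days before the cut-off has reached the target day, but their visit may not be due for another two weeks.

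Deaths and survival reach the database by different routes. Protocol 12.5 makes every death an SAE, reportable within 24 hours of the site learning of it. For a discharged subject, survival after Day 29 is assessed at the Day 60 and Day 90 contacts. The Day 60 contact ends by Day 74, nine days before the window opens at Day 83. A discharged survivor who has kept every appointment can therefore have no qualifying alive date, while a death in the same group is already recorded. None of the three alive rules in Section 5.7.2 covers that survivor.

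Day 90 mortality appears at the same lock as the primary result. Its denominator, and the status of the pending subjects, would be left to the programmer.

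**Working it through.** **Step 1: reproduce the 90-day rule.** Let g be the days from randomization to dosing, 0 or 1 under the 24-hour rule (SAP 4.2.2 gives g = 0 for undosed subjects). Study Day X falls g + X − 1 days after randomization.

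| Study day | g = 0 | g = 1 |
|---|---|---|
| 74 (end of Day 60 contact) | 73 | 74 |
| 83 (window opens) | 82 | 83 |
| 90 (target) | 89 | 90 |
| 104 (window closes) | 103 | 104 |

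Ninety days from randomization guarantees that the target day has been reached, and no more.

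**Step 2: the shortfall.** 103 − 90 = 13 days with same-day dosing; 104 − 90 = 14 days with next-day dosing.

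**Step 3: subjects in the gap.** Phase 3 Cohort 1 randomized 581 subjects (SAP 1.4). The accrual period is not stated, so I assume even accrual over T days and a cut-off 28 days after the last randomization.

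- Set under the 90-day rule: (581/T) × (T + 28 − 90)
- Set under a 104-day rule: (581/T) × (T + 28 − 104)
- Gap: (581/T) × 14

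| T (days) | 90-day set | 104-day set | Gap | Share of 90-day set |
|---|---|---|---|---|
| 180 | 381 | 336 | 45 | 11.9% |
| 240 | 431 | 397 | 34 | 7.9% |
| 300 | 461 | 434 | 27 | 5.9% |
| 365 | 482 | 460 | 22 | 4.6% |

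A cut-off four days later leaves the gap counts unchanged (set sizes 394 to 489, shares 11.5% to 4.6%). These counts are upper bounds: they include recorded deaths and survivors who already have a record from Day 83 on.

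**Step 4: effect on the mortality figure, by handling.**

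*Kept in the denominator and counted alive.* Everyone in the set has reached Day 90, so every death by Day 90 has already occurred. Only a death the site has not yet learned of is missed. One such death lowers that arm's figure by 1/(381/3) = 1/127 = 0.79 percentage points for the smallest set, or 1/(482/3) = 1/161 = 0.62 points at T = 365. The documents give no basis for estimating how many there would be.

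*Dropped from the denominator.* With true mortality p, gap share s and a fraction u of gap survivors unconfirmed, the reported rate is p / (1 − s(1 − p)u), assuming equal mortality inside and outside the gap and all deaths recorded. For an assumed p = 15%:

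- s = 0.05, u = 0.25: 0.15 / (1 − 0.05 × 0.85 × 0.25) = 15.2%
- s = 0.12, u = 1: 0.15 / (1 − 0.12 × 0.85) = 0.15 / 0.898 = 16.7%

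**The case against.** The strongest reply is that little can go wrong.

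- **Confirmation does not need a visit.** SAP 4.2.4 takes the last date of any subject record, so an adverse event, medication or hospital record from Day 83 on is enough. Inpatients are assessed daily. This stands, and it is why the counts above are only ceilings.
- **The plan does not drop anyone.** Section 4 bases percentages on the analysis set. A reader might infer that first-lock Day 90 mortality is inflated because deaths count and pending survivors do not. The documents do not support that: inflation needs an exclusion that the SAP nowhere states.
- **The cut-off wording is not a contradiction.** A reader might infer that Section 3.4 relies on a date the SAP says is not used. However, Section 4.6 allows for exceptions and then lists Day 90 mortality, and Section 6 speaks only of the main analyses. Section 3.4 can stand as an exception. What remains is that the date is never defined.
- **The output carries limited weight.** Day 90 mortality is outside the four tested families (SAP 5.7.1), and the ITT analysis follows at the second lock. The figure may change then anyway, because later-randomized subjects join.
- **A 104-day rule discards some known outcomes** and does not settle a subject overdue beyond Day 104, who under Protocol 7.3.4 is not lost to follow-up until the end of the study. This is correct, so the date change needs an accompanying rule for unknown status.

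The reply does not remove the missing outcome for an on-study subject last seen before Day 83. Nor does it explain why first-lock Day 90 TEAE tables are confined to subjects with complete TEAE data to Day 90 (Section 4.6) while mortality has no matching condition. The Phase 2 SAP (4.4) planned a survival sweep before lock; Section 4.4 of the Phase 3 SAP has none.

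**Conclusion.** The point holds as a limited defect in one output: Day 90 mortality for Phase 3 Cohort 1 at the first lock. Cohort 2 has a single lock and is not affected. The entry rule is 13 to 14 days short of the SAP's own window, the cut-off date is undefined, and Section 5.7.2 leaves one class of subject without an outcome.

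At most about 22 to 45 subjects, 5% to 12% of the set, are exposed, assuming even accrual over 6 to 12 months; the number actually unconfirmed is unknown. The effect on the mortality figure is probably small. Under the denominator that Section 4 implies, the direction of risk is understatement from deaths not yet known to the site. The Day 29 conclusions do not depend on this set, and neither does the second-lock ITT analysis.

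One limit applies: Phase 3 SAP Sections 2.1 to 2.3 and Table 1 are not legible in the public copy, so a Day 90 definition placed there could not be checked.

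**What to change.** 1. In SAP 3.4, replace 90 days with at least 104 days from randomization to the cut-off. This covers the whole window for same-day and next-day dosing.
2. State a calendar cut-off date for first-lock Day 90 outputs, and say in Sections 4.6 and 6 that these outputs are the exception to the subject-level Day 29 rule.
3. Add to Section 5.7.2 how a subject who is still on study, not known to have died and without a record from Day 83 on is counted. This is needed even with the 104-day rule, for overdue contacts.

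A survival sweep before the first lock, as in the Phase 2 SAP, would be a useful addition.

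The cost is SAP wording and an interim subset about 5% to 12% smaller under the assumed accrual (for example, 336 instead of 381, or 460 instead of 482). Some outcomes already known at the first lock would wait for the second. The second-lock analysis does not change.
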